5.8.2 Withdrawal from the Trial

Subjects may withdraw from the trial at any time for any reason. If a subject withdraws from the trial, they will no longer receive treatment or be followed at scheduled protocol visits.

A subject must be withdrawn from the trial if:

- The subject or legal representative (such as parent or legal representative) withdraws consent from the trial.
- The subject is lost to follow-up.

Specific details regarding procedures to be performed at the time of withdrawal from the trial including specific details regarding withdrawal from Future Biomedical Research are outlined in Section 7.1.4 – Other Procedures.

5.9 Subject Replacement Strategy

A subject who discontinues from treatment or withdraws from the trial will not be replaced.

5.10 Beginning and End of the Trial

The overall trial begins when the first subject signs the informed consent form. The overall trial ends when the last subject completes the last study-related phone-call or visit, withdraws from the trial or is lost to follow-up (i.e. the subject is unable to be contacted by the investigator).

5.11 Clinical Criteria for Early Trial Termination

Early trial termination will be the result of the criteria specified below:

5.11.1 Criteria for Assessing Safety in the First 50 Subjects

The following criteria apply to stopping further allocation after the first 50 subjects have commenced treatment, and not continuing allocation to reach the overall target of n=250.

These criteria will be assessed after the last of the first 50 subjects reaches TW4, as this allows for steady state of drug to be achieved for ≥ 2 weeks.

If >3 out of the first 50 subjects receiving MK-3682 + RZR experience any of the following, study therapy will be discontinued in all subjects and no additional subjects will be enrolled or allocated to treatment.

- The subject has a Grade 4 laboratory abnormality, or a life-threatening clinical AE, or an AE that results in or prolongs an existing hospitalization, or death, that is assessed to be study drug related.
- The subject's ALT or AST increases to >500 IU/L, is assessed to be study drug related, and is not associated with virologic failure.
- The subject's serum creatinine increases to Grade 3 or higher (>1.8 × ULN), confirmed with repeat test within 1 week, that is assessed to be study drug related.
- The subject's creatinine clearance (eGFR) decreases to <50 mL/min/1.73 m², confirmed with repeat test within 1 week, that is assessed to be study drug related.

Note: Creatinine clearance will be evaluated as an eGFR based on the modification of diet in renal disease (MDRD) equation:

$$\text{eGFR (mL/min/1.73 m}^2\text{)} = 175 \times (\text{Scr, std})^{-1.154} \times (\text{Age})^{-0.203} \times (0.742 \text{ if female}) \times (1.212 \text{ if black})$$

Scr, std: serum creatinine measured with a standardized assay

5.11.2 Safety Criteria for Stopping Enrollment/Allocation At Any Time During the Trial

If >12 subjects receiving MK-3682 and RZR, at any time during the trial, experience any 1 of the following, the trial will terminate.

- The subject has a Grade 4 laboratory abnormality, or a life-threatening clinical AE, or an AE that results in or prolongs an existing hospitalization, or death, that is assessed to be study drug related.
- The subject's ALT or AST increases to >500 IU/L, is assessed to be study drug related, and is not associated with virologic failure.
- The subject's serum creatinine increases to Grade 3 or higher (>1.8 × ULN), confirmed with repeat test within 1 week, that is assessed to be study drug related.
- The subject's creatinine clearance (eGFR) decreases to <50 mL/min/1.73 m², confirmed with repeat test within 1 week, that is assessed to be study drug related.

Note: Creatinine clearance will be evaluated as an eGFR based on the modification of diet in renal disease (MDRD) equation:

$$\text{eGFR (mL/min/1.73 m}^2\text{)} = 175 \times (\text{Scr, std})^{-1.154} \times (\text{Age})^{-0.203} \times (0.742 \text{ if female}) \times (1.212 \text{ if black})$$

Scr, std: serum creatinine measured with a standardized assay

5.11.3 Safety Criteria for Pausing Enrollment/Allocation

If ≥3 subjects receiving MK-3682 and RZR experience any of the following during the study, treatment allocation will be paused:

- The subject has a Grade 4 laboratory abnormality, or a life-threatening clinical AE, or an AE that results in or prolongs an existing hospitalization, or death, that is assessed to be study drug related.

Subjects who are tolerating treatment may continue to receive study therapy, but no additional subjects will be allocated to treatment until the Sponsor has reviewed all safety data on subjects.

5.11.4 Efficacy Criteria for Stopping Enrollment/Allocation

The efficacy criteria for stopping enrollment/treatment allocation are:

1. A total of ≥ 3 out of the first 10 subjects in the per-protocol (PP) population (see Section 8.5.1 for definition) for each GT (GT1-6) receiving 12 weeks of therapy experience virologic failure (non-response, rebound, breakthrough, or relapse) by FW4, or
2. >5 subjects in the PP population for GT1-4, and >3 subjects in the PP population for GT5-6, experience virologic failure at any point in the trial.

If either of these criteria is met, then no additional subjects of that particular GT would be allocated to treatment in the trial. Additionally, the Sponsor will review the results, and if the majority of failures are due to relapses (i.e., $>50\%$), the treatment regimen will be modified for all subjects of that GT still on treatment. If the treatment regimen is modified, the duration will be extended to 16 weeks and RBV will be added to the regimen (investigators will review considerations and contraindications to RBV with subjects impacted).

Criteria for HIV-infected Subjects

If a total of ≥ 2 HIV-infected subjects across all arms experience confirmed loss of HIV-1 virologic suppression at any time, then no additional HIV co-infected subjects will be enrolled. Loss of virologic suppression is defined as HIV-1 RNA ≥ 200 copies/mL, confirmed on 2 consecutive tests at least 2 weeks apart in subjects compliant with their HIV ARV therapies. Remaining co-infected subjects who are already on trial treatment will continue their assigned HCV treatment regimen while their HIV regimen is being reassessed.

6.0 TRIAL FLOW CHART

Trial Period		Treatment Period														Follow-up Period						Unscheduled	
Visit Number	1	2	3	4	5	6	7	8	9	10	11	12	13	14	15	16	17	18	19	20	21	22	
Intensive PK/PD group:	Screening	Day 1 ¹	Day 2	Day 3	Day 5	Day 7	TW2	TW4	TW6	TW8	TW10	TW12	TW14 ²	TW16 ²	FW 4	FW 8	FW 12	FW 16	FW 20	FW 24	Viral Failure Confirmation (HCV or HIV)	Early Discontinuation Visit	
Main Study Group			n/a	n/a	n/a																		
Visit Window	-45d	n/a	n/a	+2d	-1d to +2d	-2d to +2d	-7 to +7 days					-7 to +14 days				-2 to +2 weeks						n/a	n/a
Administrative Procedures																							
Informed Consent	X																						
Informed Consent for Future Biomedical Research	X																						
Inclusion/Exclusion Criteria	X																						
Subject Identification Card	X	X																					
Medical History	X																						
Prior & Concomitant Medication Review ³	X	X				X	X	X	X	X	X	X	X	X	X	X	X	X	X	X	X	X	
Treatment Allocation		X																					
Study Medication Diary: Distribute and/or and Review Instructions		X	X	X	X	X	X	X	X	X	X	X	X	X								X	
Reconcile Study Medication/Assess Compliance			X	X	X	X	X	X	X	X	X	X	X	X									
Telephone Contact																		X	X				
Clinical Procedures/Assessments																							
Comprehensive Physical Examination ⁴	X																						
Focused PE ⁴		X	X	X	X	X	X	X	X	X	X	X	X	X	X	X	X				X	X	
Height		X																					
Weight		X																					
12-Lead Electrocardiogram	X	X		X ⁵		X ⁵	X	X		X		X			X		X						
Vital Signs (heart rate, blood pressure, temperature)	X	X	X	X	X	X	X	X	X	X	X	X	X	X	X	X	X				X	X	
Subject Confirmation of Birth Control	X	X					X	X	X	X	X	X	X	X	X	X ⁶	X ⁶				X ⁶	X ⁷	
Review Adverse Events ⁸	X	X	X	X	X	X	X	X	X	X	X	X	X	X	X	X	X	X	X	X	X	X	

Trial Period	Treatment Period														Follow-up Period						Unscheduled		
Visit Number	1	2	3	4	5	6	7	8	9	10	11	12	13	14	15	16	17	18	19	20	21	22	
Intensive PK/PD group:			Day 2	Day 3	Day 5																Viral Failure Confirmation (HCV or HIV)	Early Discontinuation Visit	
Main Study Group	creening	Day 1 ¹	n/a	n/a	n/a	Day 7	TW2	TW4	TW6	TW8	TW10	TW12	TW14 ²	TW16 ²	FW 4	FW 8	FW 12	FW 16	FW 20	FW 24			
Visit Window	-45d	n/a	n/a	+2d	-1d to +2d	-2d to +2d	-7 to +7 days					-7 to +14 days			-2 to +2 weeks						n/a	n/a	
Laboratory Safety Evaluations																							
Chemistry & Hematology	X	X				X	X	X	X	X	X	X	X	X	X	X	X				X	X	X
Urinalysis	X	X				X	X	X	X	X	X	X	X	X	X	X	X				X	X	X
Coagulation	X	X				X	X	X	X	X	X	X	X	X	X	X	X				X	X	X
Urine Pregnancy Test (females of child bearing potential only) ⁹	X	X					X	X	X	X	X	X	X	X	X	X ⁶	X ⁶				X ⁶	X ⁷	X ⁷
HBV Evaluations¹⁰																							
HBsAg	X	X						X		X		X		X	X		X				X		
Anti-HBc	X																						
Anti-HBs	X																						
HBV DNA	X	X						X		X		X		X	X		X				X		
Pharmacokinetics¹¹																							
MK-3682 and Metabolites		X		X ¹¹		X ¹¹	X	X	X	X		X		X							X ¹²	X ¹²	
RZR		X		X ¹¹		X ¹¹	X	X	X	X		X		X							X ¹²	X ¹²	
Meal Information for PK		X		X ¹¹		X ¹¹	X	X	X	X		X		X							X ¹²	X ¹²	
HCV Evaluations																							
HCV RNA ¹³	X	X	X ¹¹	X ¹¹	X ¹¹	X	X	X	X	X	X	X	X	X	X	X	X				X	X	X ¹⁴
HCV Genotype Determination	X																						
Liver Imaging ¹⁵	X																						
Plasma for HCV Viral Resistance ¹⁶		X													X	X	X				X	X	X ¹⁴
Blood for genetic analysis ¹⁷		X																					
HIV Evaluations¹⁸																							
HIV Serology	X																						
HIV RNA	X	X				X	X	X	X	X	X	X	X	X	X	X	X				X		X
Plasma for HIV Viral Resistance																					X ¹⁹		
CD4+ T-cell Count	X	X				X	X	X	X	X	X	X	X	X	X	X	X				X		X
Drug Administration²⁰																							
Dispense MK-3682 (open-label)		X						X		X		X											
Dispense RZR (open-label)		X						X		X		X											
Only if treatment duration is extended, dispense RBV (open-label)		X						X		X		X											

AE = adverse event; anti-HBc = hepatitis B core antibody; anti-HBs = hepatitis B surface antibody; d = day; DNA = deoxyribonucleic acid; FBR = future biomedical research; FU = Follow-up; FW = Follow-up Week; HBsAg = hepatitis B surface antigen; HBV DNA = hepatitis B virus deoxyribonucleic acid; HCV = hepatitis C virus; HIV = human immunodeficiency virus; IRB/IEC = Institutional Review Board/Independent Ethics Committee; n/a = not applicable; PD = pharmacodynamics; PE = physical examination; PK = pharmacokinetics; RBV = ribavirin; RNA = ribonucleic acid; RZR = ruzasvir; TW = Treatment Week

- 1 Procedures on Visit 2, Day 1 should be performed prior to the first dose unless specified otherwise.
- 2 **TW14 and TW16 will only occur for those subjects whose treatment duration may be extended. PK sample scheme for these subjects remain the same with the addition of TW16 time point.**
- 3 Non-study HCV medications/therapies are prohibited through FW24. Any use should be reported throughout the subject's participation in the trial.
- 4 A comprehensive PE will be done at screening. For all other visits, a focused PE will be conducted when clinically indicated.
- 5 Additional ECGs will be collected on subjects in the Intensive PK/PD group at Day 3 and Day 7.
- 6 This procedure only applies to female subjects of child bearing potential whose treatment regimen is modified to include RBV.
- 7 This procedure is performed only when the visit occurs prior to FW4. For female subjects of child bearing potential whose treatment regimen is modified to include RBV, urine pregnancy test and birth control confirmation should be performed when the visit occurs anytime through FW24.
- 8 All AEs that occur after the consent form is signed but before treatment allocation must be reported by the investigator if they cause the subject to be excluded from the trial, or are the result of a protocol-specified intervention, including but not limited to washout or discontinuation of usual therapy, diet, placebo treatment, or a procedure. From the time of treatment allocation through 14 days following cessation of treatment, all AEs must be reported by the investigator. The reporting timeframe for AEs meeting any serious criteria is described in Section 7.2.3.1.
- 9 For subjects whose treatment regimen is modified to include RBV, when study visits are spaced more than 1 month apart in the follow-up period, urine pregnancy test kits will be dispensed to female subjects of childbearing potential so that monthly pregnancy testing can continue for 6 months after dosing (or longer if dictated by local regulations). The test results must be provided to the investigator and/or site personnel. Subjects should be instructed to contact the investigator and/or site personnel immediately if the result of the self-pregnancy test is positive. A serum pregnancy test will be performed whenever a urine pregnancy test yields a positive result.
- 10 HBsAg, anti-HBc, and anti-HBs will be assessed at screening in all subjects. For all anti-HBc positive subjects, HBV DNA will also be assessed at screening, and both HBV DNA and HBsAg will be monitored during the trial.
- 11 PK samples will be collected as described in Section 7.1.3.2. Only subjects in the Intensive PK/PD group will have PK samples collected on Day 3, and post dose on Day 7. These subjects will also have additional HCV RNA samples collected postdose on Day 1-2, Day 3, and Day 5.
- 12 PK samples and meal information for PK are to be collected at HCV/HIV viral confirmation or early discontinuation visits that occur only during the study treatment period.
- 13 Leftover main study plasma will be stored at the end of the study for FBR if the subject consents to FBR.
- 14 If a subject is a confirmed viral failure during therapy (i.e., breakthrough), then sample collection for HCV RNA and Viral Resistance/Biomarker is not needed for the early discontinuation visit.
- 15 For cirrhotic subjects only, imaging is required within 6 months of randomization to evaluate for hepatocellular carcinoma. If liver imaging within 6 months prior to Day 1 is not available, imaging is required during screening.
- 16 Blood samples will be collected for HCV viral resistance testing at Day1, virologic failure confirmation visits, and all follow-up visits after virologic failure confirmation or after early study medication discontinuation if the subject has quantifiable HCV RNA and is not the result of a virologic failure during therapy (i.e., rebound, breakthrough). Leftover main study plasma will be stored at the end of the study for FBR if the subject consents to FBR.
- 17 This sample will be drawn for IL28B genotyping and for planned analysis of the association between genetic variants in DNA and drug response. If the IRB/IEC does not approve of the planned analysis of the association between DNA variation and drug response, or if there is a local law or regulation prohibiting the same, data analysis will be limited to IL28B. Leftover extracted DNA will be stored for FBR if the subject signs the FBR consent.
- 18 HIV serology (HIV-1 and HIV-2) will be performed at screening for all subjects. HIV RNA and CD4+ T cell count at screening will only be processed for those subjects who have positive HIV serology. HIV evaluations will only be performed at Day 1 and subsequent visits as indicated in subjects that are HIV co-infected.
- 19 In subjects who are HIV co-infected, blood samples will be collected for HIV viral resistance at the time of HIV RNA failure confirmation visit.

- ²⁰ Study medication will be dispensed at Day 1 and then every 4 weeks thereafter: Week 4 and Week 8. If the treatment regimen is extended, MK-3682 + RZR also will be dispensed at Week 12. RBV should be locally sourced and dispensed by the site if the treatment regimen is extended. Note that the duration of treatment with MK-3682 + RZR for subjects with a particular GT may be extended to 16 weeks' duration and RBV added to the regimen if the efficacy criteria for stopping enrollment/treatment allocation are met for that particular GT. For example, if efficacy criteria for stopping enrollment/treatment allocation are met for GT1-infected subjects at TW8, GT1-infected subjects already on treatment will receive MK-3682 + RZR for an additional 8 weeks (i.e., 16 weeks' total duration) + RBV for 8 weeks.

All doses of MK-3682 and RZR should be taken on an empty stomach after an overnight fast, at least 1 hour before the morning meal. Study medications should be taken with water but without food. In addition, subjects should fast overnight prior to reporting to the study site for dosing on Treatment Day 1 (Visit 2) and for all other visits at which a pre-dose PK sample is to be collected. MK-3682 and RZR (open-label) will be provided by the Sponsor to cover a maximum of 32 days of dosing (4 weeks + 4 days). An unscheduled visit must occur to get additional drug if the subject will run out of study drug prior to the next scheduled visit. If dosing is missed or interrupted (see Section 5.2.2), the assigned study therapy regimen should still be completed.

For subjects whose treatment regimen is modified to include RBV, RBV is to be dosed according to the approved local prescribing information.

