 - a) The subject is a male who is not of reproductive potential, defined as a male who has azoospermia (whether due to having had a vasectomy or due to an underlying medical condition).
 - b) The subject is a female who is not of reproductive potential, defined as a female who either: (1) is postmenopausal (defined as at least 12 months with no menses in women ≥ 45 years of age); (2) has had a hysterectomy and/or bilateral oophorectomy, bilateral salpingectomy, or bilateral tubal ligation/occlusion at least 6 weeks prior to screening; OR (3) has a congenital or acquired condition that prevents childbearing.
 - c) The subject is a female or a male who is of reproductive potential and agrees to avoid becoming pregnant or impregnating a partner beginning at least 2 weeks prior to administration of the initial dose of study drug, and for **6 months after taking the last dose** of study drug (or longer if dictated by local regulations) by complying with 1 of the following: (1) practice abstinence[†] from heterosexual activity OR (2) use (or have their partner use) **2** forms of acceptable contraception during heterosexual activity. Acceptable methods of contraception are as follows[‡]:
 - intrauterine device (with or without local hormone release)
 - diaphragm with spermicide (cannot be used in conjunction with cervical cap/spermicide)
 - cervical cap with spermicide (nulliparous women only)
 - contraceptive sponge (nulliparous women only)
 - male condom with spermicide or female condom with spermicide (cannot be used together)
 - hormonal contraceptive: oral contraceptive pill (estrogen/progestin pill or progestin-only pill), contraceptive skin patch, vaginal contraceptive ring, or subcutaneous contraceptive injection

If male, subjects must agree to use a condom with spermicide or abstain from sexual intercourse during the trial until **6 months after taking the last dose** of study drug (or longer if dictated by local regulations).

Spermicides alone are not an acceptable method of contraception.

Subjects must be completely informed of the unknown risks of pregnancy and agree not to become pregnant during the time they are participating in this trial.

If there is any question that a subject will not be reliable in the use of appropriate contraceptive methods, they should not be entered into the trial.

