7.1.2.5 Birth Control Confirmation

Care must be taken to avoid pregnancy in female subjects of childbearing potential, and for the female partners of childbearing potential of male subjects, who have their treatment regimen with MK-3682 + RZR extended to 16 weeks' duration and RBV added to the regimen.

Confirmation must be obtained by site personnel that subjects and their partner(s) are using acceptable methods of contraception (see Subject Inclusion Criteria, Section 5.1.2). This assessment must be documented in the subject's study chart at each specified visit (see Trial Flow Chart, Section 6.0).

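### Flow Chart footnotes 6 and 7 give ribavirin-treated men no scheduled contraception check after Follow-up Week 4, although their contraception duty runs for 6 months after the last dose

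*Combined protocol and SAP*

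**What the plan says.** **The duty.** Criterion 6 in Section 5.1.2 states: "If male, subjects must agree to use a condom with spermicide or abstain from sexual intercourse during the trial until" six months after the last dose. Its note shortens the period to 14 days, but only for subjects never given RBV. Section 7.1.5.1 likewise sets 6 months for any subject extended with RBV and makes no distinction by sex.

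**The check.** Section 7.1.2.5 deals with subjects whose regimen is extended with RBV. It calls for care to avoid pregnancy in women and "for the female partners of childbearing potential of male subjects". It then says: "Confirmation must be obtained by site personnel that subjects and their partner(s) are using acceptable methods of contraception". It sets no visits of its own; the assessment goes in the "study chart at each specified visit (see Trial Flow Chart, Section 6.0").

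**The schedule.** In the Flow Chart, the row "Subject Confirmation of Birth Control" has plain marks up to and including FW4. The later follow-up marks carry footnote 6: "This procedure only applies to female subjects of child bearing potential whose treatment regimen is modified to include RBV". At unscheduled visits, footnote 7 confines the procedure to visits before FW4. For women of childbearing potential on RBV it adds that "urine pregnancy test and birth control confirmation should be performed when the visit occurs anytime through FW24". The same two footnotes serve the row "Urine Pregnancy Test (females of child bearing potential only)".

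**The concern.** The text puts ribavirin-treated men and their partners within the check, and the chart that supplies the visits leaves them out after FW4. An FW4 cut-off suits a regimen without RBV, where the duty ends at 14 days. It does not suit a 6-month duty. The restriction to women is right for a urine pregnancy test but not for a question about contraception.

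At stake is a fetal-safety precaution. A lapse in contraception in a ribavirin-treated man after FW4 would not be asked about, even at visits he attends anyway. The protocol itself treats exposure through the male partner as a risk: exclusion 11 bars men with pregnant partners because of RBV, and exclusion 10 bars men who expect to donate sperm within 6 months of the last dose.

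**Working it through.** The plan states no figure for this gap, so the check compares the provisions and then uses calendar arithmetic.

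**Step 1. Which marks in the birth control row apply to whom (RBV-treated subjects)**

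| Contact | Women of childbearing potential | Men |
|---|---|---|
| Screening, Day 1, TW2 to TW16, FW4 | yes | yes |
| FW8, FW12 | yes (footnote 6) | no |
| FW16, FW20 (telephone) | no mark | no mark |
| FW24 | yes, on the aligned reading | no |
| Unscheduled, before FW4 | yes | yes |
| Unscheduled, FW4 through FW24 | yes (footnote 7) | no |

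The extracted row appears shifted by a column near its end. The third footnote-6 mark is read as FW24 by analogy with the pregnancy test row. If it belongs under the viral failure confirmation visit instead, the result for men is unchanged, because every mark after FW4 carries footnote 6 or 7.

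**Step 2. Time without a scheduled check in men**

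- Six months: 365.25 / 2 / 7 = 26.1 weeks.
- Last check that applies to men: FW4, nominally week 4.
- Time remaining: 26.1 − 4 = 22.1 weeks, and 22.1 / 26.1 = 85% of the post-treatment period.

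**Step 3. Sensitivity to the FW4 window.** The two halves of the extracted chart place the window differently.

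- Second half, −2 to +2 weeks (FW4 at week 2 to 6): 26.1 − 6 = 20.1 to 26.1 − 2 = 24.1 weeks (77% to 92%).
- First half, −7 to +14 days (FW4 at week 3 to 6): 26.1 − 6 = 20.1 to 26.1 − 3 = 23.1 weeks.

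**Step 4. The same two measures before and after the change**

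- Time after the last scheduled check: 22.1 weeks before; 26.1 − 24 = 2.1 weeks after.
- Longest interval without a check through FW24: 24 − 4 = 20 weeks before; 24 − 12 = 12 weeks after.

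**Step 5. Share of the whole duty.** Criterion 6 starts at least 2 weeks before the first dose. For a man extended to 16 weeks the duty lasts 2 + 16 + 26.1 = 44.1 weeks, and the unchecked part is 22.1 / 44.1 = 50%.

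**The case against.** The best defence is that nothing strictly contradicts. Section 7.1.2.5 hands the timing to the chart, the chart specifies the visits, and the 6-month duty on men stays in force whether or not anyone asks again. How often to re-ask men who are off treatment is a monitoring choice. Other safeguards also remain:

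- the agreement at entry, and refusal of entry where reliability is in doubt;
- exclusions 10 and 11;
- instruction at screening;
- review of RBV contraindications when the regimen is changed (Section 5.11.4);
- checks through FW4;
- reporting of partner pregnancies for 6 months on RBV (Section 7.2.2);
- extra procedures where clinically necessary (Section 7.1).

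This shows that men are not unprotected, and it lowers the weight of the point. It does not close the gap, since none of these is a scheduled check after FW4.

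A reader might infer more than the documents support:

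- **That 26 weeks is the whole duty.** It is only the part after the last dose; the whole is about 44 weeks, and men are checked in the earlier part.
- **That men miss all five later contacts because of the footnotes.** FW16 and FW20 are telephone calls with no mark in this row for either sex. The footnotes withhold at most three scheduled checks.
- **That partner pregnancies go uncaptured because of the footnotes.** The row never asks men about partner pregnancy, even before FW4; Section 7.2.2 covers it.
- **That the limit was copied by mistake from the pregnancy test row.** Sharing the footnotes makes this plausible, but footnote 7 names birth control confirmation expressly, so an error is not shown.

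**Conclusion.** The point holds as a minor safety-consistency fix. On the chart as written, ribavirin-treated men have no scheduled contraception check for about 22 of the 26 weeks after the last dose (20 to 24 across the possible FW4 windows). They lose up to three scheduled checks that ribavirin-treated women receive, and the unscheduled-visit checks from FW4 through FW24. This is a written exclusion rather than a silence, and no other section schedules a check to replace it.

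The figures assume a nominal 6 months of 26.1 weeks. The count of three, and the women's FW24 check, rest on the aligned reading of the row; the absence of checks in men does not.

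The gap needs a genotype to meet an efficacy stopping criterion, more than half of its failures to be relapses, and men of that genotype still to be on treatment. The documents give no sex split, so the number affected is unknown and may be zero. A reader might infer an effect on the trial's results; there is none, because no efficacy endpoint or analysis uses this row.

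**What to change.** Give the birth control confirmation row its own wording of footnotes 6 and 7. It should cover all subjects of reproductive potential, male or female, whose regimen is modified to include RBV. State FW8, FW12, FW24 and unscheduled visits through FW24 explicitly, which also settles the column alignment. Leave the urine pregnancy test row, with its present footnotes, for females only.

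Asking men about partner pregnancy at the same visits is an optional addition. It would support reporting under Section 7.2.2 but is not part of the footnote repair.

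The cost is two footnote edits and one question, or two with the option, at visits already scheduled or already taking place. No new visit, call or sample is needed.
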